1.0 Rationale

Chronic obstructive pulmonary disease, also known as COPD, is a debilitating disease that affects a growing percentage of the Canadian population (Public Health Agency of Canada, 2007). COPD is characterized by chronic and progressive airflow limitations causing shortness of breath, chronic cough, and sputum production (Public Health Agency of Canada, 2008). COPD includes chronic bronchitis and emphysema, as well as other similar respiratory illnesses and is primarily caused by smoking cigarettes, though other causes do exist (Public Health Agency of Canada, 2008). The airflow limitation can affect oxygen transfer in the lungs, increasing the effort required to perform activities of daily living such as: walking, climbing stairs, and gardening (Annegarn et al., 2012). To date, COPD is not fully reversible, but various treatments (e.g., exercise, medications) are available to help manage the disease. Approximately 4% of the Canadian population report being diagnosed with COPD; however, 13% of Canadians were found to have a lung function score indicative of COPD (Statistics Canada, 2013). It is believed that COPD will become the third leading cause of death by 2030, and according to the last World Health Organization estimate in 2004, 64 million people are currently living with COPD (World Health Organization, 2015).

COPD has a large impact on the well-being and quality of life of patients living with the disease. Individuals living with COPD are aware of their worsening well-being and quality of life (Disler et al., 2014). They are required to make drastic lifestyle changes in order to minimize lung function declines. These lifestyle changes include smoking cessation, adoption of an exercise program to maximize oxygen transfer in muscle and reduce whole body oxygen demands, and an extensive medication regime (George, Kong, Thoman, & Stewart, 2005). Patients mostly rely on their health care providers to present them with the necessary information about their disease and how to modify their lifestyle. However, patients appear to have different expected outcomes from COPD interventions compared to their health care providers; such as, for end of life care (Cooke & Campbell, 2014). These conflicting expectations can reduce the positive impact that providers can have on their patients. For this reason it has become critical to understand the patients' perspectives and priorities related to their health care, as well as, to the COPD research that may influence their care. In fact, it is not until recently that patient involvement in health research has become recognized as an important next step to identify the outcomes that matter most to

individuals who are diagnosed with COPD (Celli et al., 2015). Recent evidence suggests that research does not necessarily align with the underlying needs of patients suffering from life-limiting illness such as COPD (Cooke & Campbell, 2014). This evidence is concerning as patient-centered outcome-focused interventions have been found to work better with COPD patients than interventions that aim to improve surrogate outcomes (Celli et al., 2015). It is now necessary to understand patients' main concerns regarding COPD (e.g., alleviate dyspnea), what they wish to see in future COPD research and what information they would like from their health care provider. It is only by getting their perspectives on these matters that we can move to enhance the well-being and quality of life of adults living with COPD. This study therefore aims to fill these critical gaps in the COPD literature.

To get a better understanding of the life domains that are most important and critical for adults with COPD, we need to identify key daily activities and examine the extent to which participating in these activities are difficult and the reasons that may hamper participation (e.g., breathlessness). To get at this understanding we have grounded the study in the International Classification of Functioning, Disability and Health (ICF) (World Health Organization, 2002) and focused on the activities and participation domains of the ICF. The ICF defines activities as "the execution of a task or action by an individual" and participation as "involvement in a life situation" (World Health Organization, 2002). Activities includes all daily activities that individuals partake in on a regular basis; such as, walking, bathing, and preparing meals. Participation focuses on social and leisure activities; such as, maintaining relationship with friends and family or accessing community services. By identifying which items in the activity and participation domain of the ICF are difficult for people living with COPD, we will be able to generate a better understanding of their needs and priorities. This knowledge could then inform health care providers and health researchers about the activities that patients want to participate in and which barriers are limiting the potential for participation. In addition, we can have a better understanding of the activities that have the most positive and/or negative impact on their well-being and quality of life.

2.0 Purpose

The overall goal of this study is to identify the priorities of individuals living with COPD in terms of their activities and participation, as well as their research priorities and health care concerns. To achieve this overall goal, the study is divided into three phases (see Figure 1). The purpose of the *first phase* is to develop and pilot test a questionnaire created for individuals living with COPD to assess their activities, participation, and health care and COPD-related research priorities. The Activities, Healthcare and Research Priorities Questionnaire (AHRPQ) was developed based on past research, then verified by a panel of COPD and participation experts to gather their opinions and recommendations. The AHRPQ was then examined by adults with COPD in focus groups, where they provided feedback on the content and readability of the questionnaire. Five focus group participants were also invited to complete the full survey online as an initial pilot test.

The purpose of the *second phase* of the study is to compare across diagnosed COPD stages and disease severity the extent to which adults with COPD participate in the listed activities and identify their primary research and health-care related priorities. The AHRPQ will be administered at three sites across Montreal where clinical data for each participant will be available. This phase will also help establish the reliability of the questionnaire.

In the *third phase*, the purpose is to administer the questionnaire to a pan-Canadian sample to identify the activities that individuals living with COPD participate in, the barriers that limit their participation in these activities, the activities that are of most importance for this population, and their health concerns and research priorities. We will also be examining the relationship between participation and quality of life related outcomes. The questionnaire will be distributed to a larger population of individuals living with COPD who self-report their COPD diagnostic/severity.

This amendment is to add the protocol for the *second phase* of the study. We presented the overall goal in order to contextualize the current application.

[figure not shown]

Figure 1: The three phases of the study, broken down into each step of the phases. The identified phase (Phase 2) is the following protocol amendment.

References

2.1 Expected Outcomes

Patients living with COPD are not always provided with sufficient information to answer their questions concerning the disease and its impact on quality of life. The debilitating nature of COPD has a large impact on the daily, social and community activities performed by people living with COPD. By gathering information on the extent to which people with COPD want to participate in various activities and the barriers to their limit their participation, we will better understand the needs of this population. This information can then be disseminated to health care providers and health researchers. A second benefit of this study is understanding the specific health topics that are most important to people living with COPD. Because health care providers are the primary source of information for this population, prioritizing these health topics can greatly improve patient care. Lastly, identifying the patients' COPD research priorities can guide future research on the domains that are most important to this population. By improving our understanding of the specific activities and topics that are prioritized by people living with COPD, we can better inform future research and hopefully improve the care and management of COPD.

The results of the study will be disseminated through conference presentations and publications in peer-reviewed journals. A lay summary will be distributed to the COPD community (e.g., through the Quebec Lung Association) and related health care professionals once the results have been finalized.

3.0 Protocol

Phase 2 of the study will take place in the participants' location of choice as they will either complete the study online or over the telephone with a research assistant.

Recruitment will take place at the three sites involved in the project, the Chest Institute at the MUHC Glen site, Mount Sinai Hospital, and the Lakeshore General Hospital. In collaboration with the COPD clinic at each site, research assistants will obtain permission to approach participants in the waiting rooms or before/after COPD rehabilitation sessions to explain the study and questionnaire package. The research assistants will then inform interested participants of three possible options to complete the questionnaire package: (a) on a tablet and onsite (e.g., in waiting room or another room nearby), (b) at home, online, (c) at home over the telephone with a research assistant. Participants who choose (a) the research assistants will provide a tablet and remain with them until the questionnaire is complete. If participants choose (b) or (c), the research assistant will collect the person's email address and/or telephone number and subsequently either email them the link to the survey or call them to complete the survey. If participants are undecided, the research assistant will give them a business card (APPENDIX C) with an email and a phone number to contact.

Across all three methods of data collection (a to c), participants will complete the screening form and consent form (APPENDIX A and B) prior to answering the questionnaire package. The screening form assesses the eligibility of potential participants by determining whether participants have been diagnosed with COPD by a health care professional, are above the age of 18 and able to read and write in English or French. Participants who consent to the study will agree to complete the questionnaire package and to provide the research team access to their medical information for comparative analyses. For participants who want to respond to the questionnaire over the telephone, the research assistant will complete the forms directly online.

Before the questionnaire package has been completed, participants will be prompted to provide their full name, date of birth and street name to gather their medical chart information. Their street name will be asked to ensure that the correct individual in the system has been identified. Participants will be compensated \$50 for their time and any inconveniences experienced by answering the questionnaire. If they choose to stop taking part in the study, they will not be compensated for the study.

The questionnaire package contains the AHRPQ (APPENDIX D) and additional questionnaires (APPENDIX E) to gather information on other aspects of their lives. Specifically, these additional questionnaires are: the Godin Leisure Time Physical Activity Questionnaire, the Medical Research Council Questionnaire on Breathlessness, the Charlson Comorbidities Index, the COPD Assessment Test, the Satisfaction with Life Questionnaire, the St. George's Respiratory Questionnaire, the Canadian Cohort Obstructive Lung Disease CanCOLD questionnaire, and demographic information (i.e., age and gender).

The information gathered from the medical charts includes participants: COPD status/severity (GOLD stage, % predicted FEV₁, FEV₁/FVC); comorbidities (confirming the self-report responses from the Charlson Comorbidities Index questionnaire (Appendix E; e.g., diabetes, cardiovascular disease, mental health, asthma)); Smoking cessation (confirming the self-reported smoking cessation answered by the participant in the Medical Research Council

questionnaire on breathlessness (Appendix E); and gather other health related information such as height and weight.

4.0 Potential harms and risks

We do not foresee any potential harms to the participants by completing the questionnaire. The participant has the right to skip any question he or she feels uncomfortable answering in the questionnaire as outlined in the consent form.

The risks of the proposed research are acceptable given the potential benefits of the research. Although there are no known risks of participating in this study, participants are informed that they do not have to answer any questions that make them uncomfortable, without providing a reason for abstaining from said question. They can leave or skip a question in the questionnaire at any time, without providing a reason, by exiting the web page containing the questionnaire or if answering by phone letting the research assistant know. There is no penalty for skipping or leaving the questionnaire.

5. 0 Confidentiality

All information presented during the study is confidential and will be available only to Drs. [name] and [name] and their research assistants. Any information obtained in connection with this study and that can be identified in connection with the participant will remain confidential and will be disclosed only with the participants' permission. The participant will also be assigned an identification number upon completing the questionnaire package. All of their data will be referred to by this identification number to ensure anonymity of all information received. We are also asking permission to access the participants' medical records, as highlighted in the consent form. Information from the medical records will be assigned the same identification number to keep the data confidential. This identification number will be used for comparative purposes only. Data collected from medical records will be entered in a database and only be connected through the participant's identification number. Therefore, after all data have been extracted they will be confidential.

Participants who complete the questionnaire online or with a research assistant will be asked to provide **their mailing information** for compensation purposes. The link provided to those who complete the questionnaire is a secure link (<https://www.surveygizmo.com/s3/3030935/COPD-questionnaire-Phase-2>) specific to the questionnaire hosted on the survey developing website SurveyGizmo. **The mailing information** collected while completing the questionnaire will be gathered on a separate survey within SurveyGizmo, and therefore, will not be linked with the data they provided. Only the principal investigators ([name] and [name]) and their research assistants will have access to the electronic and hard copies of the study material. **Participants mailing information will also be used to confirm participants medical chart information if there is more than one individual with the same name.**

The results from this study will be published in academic journals, presented at scientific conferences, and distributed to related health care professionals and the COPD community. The participants name will not be disclosed in either of these circumstances. **Information collected will be erased seven years after the publication of the results.**

5.1 Data storage

All data used for analyses and reporting purposes will be unidentified and replaced with identification numbers. Only Drs. [name] and [name] and their research assistant will have access to the list of identification numbers. The list will be stored in a password-protected file on password-protected computer in a locked office in Currie Gymnasium (room 235/236) at McGill University. The questionnaire information will be stored on the SurveyGizmo servers (with project data encryption) and later downloaded to a password protected computer/laptop for data analyses purposes. Medical chart information will be stored in a password protected file on a password protected computer/laptop. Only the principle investigators ([name] and [name]) as well as their research assistants will have access to the questionnaire data and medical chart information gathered. The mailing information, used for compensation purposes and to confirm the participant's identity in the medical charts, will be stored in a password protected file on a password protected computer/tablet for seven years after the study has been published.

Data will be stored for seven years after the publication of the results of the study. After this time, electronic data will be completely deleted from the computers.

5.2 Exceptions of confidentiality

Any information provided by the participants will be kept confidential. Identifiable information will only be used to gather participant specific information. Participant confidentiality will be maintained except for the **mailing information** provided by the participants to the research team. Participants mailing information will be provided to McGill Finance and will not be attached to any submitted questionnaire data. **McGill Finance will be provided the mailing information of the participants for compensation purposes only.** This mailing information data will be used to compensate participants for their time and any inconvenience; as well as, **confirm the participants in the medical charts in the event multiple people have the same name.** Any other information will only be shared with the principle investigator ([name] and [name]) and their research assistants.

6.0 Informed consent process

Individuals who are interested in participating in the study on site will be provided with a tablet to answer the questionnaire and will read the consent form prior to answering the questionnaire. They will be providing consent online, by selecting next when presented with the statement **"By clicking on the Next button below you are consenting to participate in this research study".**

Those who chose to answer the questionnaire at home online will be provided with a secure link to the consent form. Individuals who complete the questionnaire online will need to provide electronic consent prior to advancing on to the questionnaire. They will read over the information

and consent letter and **click the Next button to indicate** consent to participate (APPENDIX B). Participants who chose to answer the questionnaire via telephone will be given the consent information either by email, mail or read the consent form by a research assistant prior to answering the consent form online. In these instances, verbal consent will be accepted.

Consent will be obtained from all participants prior to completing the questionnaire online or over the telephone.

Project Title: Patients with COPD preferences, activities, and participation survey

NCT Number: NCT02970422

Principal Investigators:

[name].

Department of Kinesiology & Physical Education, Faculty of Education, McGill University.

[contact] [name]

Email: [contact]

[name].

Department of Kinesiology & Physical Education, Faculty of Education, McGill University.

[contact] [name]

Email: [contact]

Statistical Analysis

To assess individuals' airflow obstruction (disease severity), quartiles of FEV_{1%predicted} were used. Quartiles of FEV_{1%predicted} were used because we could not confirm that individuals' spirometry was done post-bronchodilator. Thus, we were unable to use the Global Initiative for Obstructive Lung Disease (GOLD) COPD staging system (23). Nevertheless, all individuals self-reported a physician diagnosis of COPD and were recruited through their healthcare providers who confirmed the diagnosis. Individuals were divided into quartiles based on their FEV_{1%} predicted, with quartiles 1, 2, 3 and 4 representing those with mild (Q1), moderate (Q2), severe (Q3) and very severe (Q4) airflow obstruction, respectively. Only individuals with a FEV₁/FVC ratio <0.70 were included in the quartiles of airflow obstruction.

Individuals' breathlessness burden and exacerbation risk groups were based on their mMRC breathlessness scores and 12-month exacerbation history (20): group A (low breathlessness + low exacerbation risk), mMRC ≤1 with ≤1 exacerbation that did not lead to

hospital admission; group B (high breathlessness + low exacerbation risk), mMRC ≥ 2 with ≤ 1 exacerbation not leading to hospital admission; group C (low breathlessness + high exacerbation risk), mMRC ≤ 1 with ≥ 2 exacerbations or ≥ 1 exacerbation that led to hospital admission; and group D (high breathlessness + high exacerbation risk), mMRC score ≥ 2 and ≥ 2 exacerbations or >1 exacerbation that led to hospital admission.

Descriptive statistics were used to report individuals' daily and social participation and provide a picture of how respondents participated in each activity. The distribution of the scores for each activity was assessed based on quartiles of airflow obstruction, breathlessness burden and exacerbation risk, sex, age, and PR participation status. Using IBM SPSS Statistical software (v.23), chi-square analysis, with standardized residuals post-hoc analyses, were performed on the participation items individually to determine if the observed value differed from the statistically expected value for quartiles of airflow obstruction, breathlessness burden and exacerbation risk, sex, age, and PR participation status. To examine the barriers and facilitators to participation, descriptive statistics were used to identify the most common barrier/facilitator. A repeated measures analysis of variance (ANOVA) was used to determine if there was a significant difference between the barrier/facilitator that was selected the most often compared to all other barriers/facilitators.

Descriptive statistics were used to report individuals' healthcare and research priorities. The distribution of the scores for each activity was assessed based on quartiles of airflow obstruction and exacerbation burden and exacerbation risk. Using IBM SPSS Statistical software (v.23), chi-square analysis, with standardized residuals post-hoc analyses, were performed to determine if the observed number of responders for each healthcare and research topics differed

from the statistically expected value for airflow obstruction and exacerbation burden and exacerbation risk. Additionally, non-parametric tests were conducted to determine if there were any between group differences for the healthcare and research topics and airflow obstruction and exacerbation burden and exacerbation risk groups. A Kruskal-Wallis non-parametric test was conducted due to the non-normality of the data, as the mean for both healthcare and research topics was skewed. Individuals giving 10% of their time/funding was the most common response for each of the healthcare or research topics. Post-hoc analyses with Bonferroni corrections were also conducted.

For the secondary outcomes, one-way ANOVAs were used to determine mean group differences. However, for both FEV1% predicted and physical activity levels, a Kruskal-Wallis non-parametric test was conducted as the data was non-normal.

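### Sample quartiles of FEV1 % predicted are named mild to very severe, so about a quarter of the analysed subset gets each name whatever its absolute level of obstruction

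*SAP*

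**What the plan says.** Protocol section 2.0 gives the purpose of the second phase as, in part, to "compare across diagnosed COPD stages and disease severity the extent to which adults with COPD participate in the listed activities". Section 3.0 lists the chart data to be extracted for this: "COPD status/severity (GOLD stage, % predicted FEV₁, FEV₁/FVC".

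The SAP (Statistical Analysis, first paragraph) describes its severity measure as "airflow obstruction (disease severity), quartiles of FEV_{1%predicted} were used". The reason given is that the spirometry could not be confirmed as post-bronchodilator. It adds: "Thus, we were unable to use the Global Initiative for Obstructive Lung Disease (GOLD) COPD staging system". The quartiles are formed within a subset: "Only individuals with a FEV₁/FVC ratio <0.70 were included in the quartiles of airflow obstruction". They are then given names, with "quartiles 1, 2, 3 and 4 representing those with mild (Q1), moderate (Q2), severe (Q3) and very severe (Q4) airflow obstruction, respectively". No FEV1 % predicted cut-points accompany the names.

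The groups are used throughout the analysis. Chi-square tests are "performed on the participation items individually to determine if the observed value differed from the statistically expected value for quartiles of airflow obstruction". The healthcare and research topics are likewise tested for departure "from the statistically expected value for airflow obstruction and exacerbation burden and exacerbation risk", and Kruskal-Wallis tests of those topics use the same grouping.

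**The concern.** Mild, moderate, severe and very severe describe an absolute degree of obstruction. A sample quartile gives only a person's position among the other people recruited. The SAP declines to stage participants and in the same paragraph attaches four severity names to groups defined by rank alone. The stated reason may justify relative groups. It cannot justify absolute names, because the quartiles are built from the same spirometry whose bronchodilator status is unconfirmed.

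What is at stake is interpretation. Severity is one of the comparisons that Phase 2 exists to make, and Protocol section 2.1 says the results will go to health care providers and researchers. A reader told that *very severe* patients favour a given topic would apply that to patients with very severe obstruction. The data would show only that the most obstructed quarter of this subset favoured it. Without the FEV1 ranges, the groups cannot be compared with those of any other cohort.

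**Working it through.** **Inputs.** From the SAP: four groups formed as quartiles of FEV1 % predicted; subset FEV1/FVC < 0.70; no stated cut-points. The documents give no FEV1 distribution, group counts or fixed FEV1 definition of the four names, so there is no figure of the plan's own to reproduce. Every value of p below, and every mean and SD, is an assumption.

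**Step 1: rank arithmetic, with no distribution assumed.** Let p be the share of the subset that meets some fixed FEV1 % predicted definition of mild. Q1 is the 25% with the highest values.

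- If p ≤ 0.25, everyone meeting the definition is in Q1. The share of Q1 not meeting it is 1 − p/0.25, which is 0.25 − p of the whole subset.
- If p > 0.25, all of Q1 meets the definition. The share of those meeting it who are named moderate or worse is (p − 0.25)/p.

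| Assumed p | Share of Q1 not meeting the definition | As share of whole subset |
|---|---|---|
| 5% | 1 − 0.05/0.25 = 80% | 20% |
| 10% | 1 − 0.10/0.25 = 60% | 15% |
| 15% | 1 − 0.15/0.25 = 40% | 10% |
| 20% | 1 − 0.20/0.25 = 20% | 5% |
| 25% | 1 − 0.25/0.25 = 0% | 0% |

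| Assumed p | Share of those meeting the definition who are named moderate or worse |
|---|---|
| 30% | 0.05/0.30 = 16.7% |
| 40% | 0.15/0.40 = 37.5% |

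As a count check, take 400 ranked people, so that Q1 is the top 100. At p = 10%, 40 people meet the definition, all of them in Q1, and the other 60 of the 100 do not. The name fits exactly only at p = 25%. The same arithmetic applies to *very severe* and Q4.

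**Step 2: the same person under different samples.** Assume FEV1 % predicted is normal. The quartile cuts are then mean ± 0.6745 × SD and the mean itself. A person at 50% predicted has z = (50 − mean)/SD.

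| Assumed mean / SD | Quartile cuts | z | Percentile | Name received |
|---|---|---|---|---|
| 35 / 10 | 28.3, 35.0, 41.7 | 1.50 | 93rd | mild |
| 50 / 18 | 37.9, 50.0, 62.1 | 0 | 50th | moderate/severe boundary |
| 65 / 18 | 52.9, 65.0, 77.1 | −0.83 | 20th | very severe |
| 75 / 12 | 66.9, 75.0, 83.1 | −2.08 | 2nd | very severe |

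In all four cases each name covers 25% of the sample, yet the same measurement runs from *mild* to *very severe*. The name is set by who was recruited.

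**The case against.** The strongest reply is that this is a labelling matter, already largely disclosed. The SAP says that quartiles were used, says why, and says GOLD staging was not possible. Each name sits beside its quartile number in one sentence, and the names do not recur when the tests are described. Rank is preserved: nobody in Q4 has a higher FEV1 % predicted than anyone in Q1. Renaming the groups alters no p-value. The size of the misnaming in this study is unknown, and its direction depends on p.

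All of that is correct, and it limits the point to interpretation. It does not rescue the names, because disclosing the method does not make a rank into an absolute grade.

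Two partial mitigations also fall short. Groups A to D rest on fixed criteria, but they measure breathlessness and exacerbation risk, not airflow obstruction. The SAP also mentions a Kruskal-Wallis test of FEV1 % predicted among the secondary outcomes, but it neither says which groups are compared nor commits to reporting each quartile's range.

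It can also be said that a continuous FEV1 analysis goes beyond what the labels require. That is fair: relabelling and reporting the ranges is the core correction. The extra analysis is supporting only, and its ordinal part depends on the questionnaire's response scale, which the SAP does not describe.

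**Conclusion.** The concern holds and should be acted on. About 25% of the FEV1/FVC < 0.70 subset (apart from ties and rounding) receives each severity name by construction, whatever its absolute level of obstruction. This follows from the definition of a quartile and needs no assumption. How far the names depart from any fixed definition cannot be determined from the documents. Over assumed p of 5% to 25%, the misnamed share of Q1 runs from 80% down to 0%; above 25% the error reverses.

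Comparisons between less and more obstructed participants remain valid. Conclusions stated in the four severity terms are not supported, and neither is presenting these results as the diagnosed-stage comparison set out in Protocol section 2.0.

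**What to change.** 1. Replace the four names with a label such as *FEV1 % predicted Q1–Q4, least to most obstructed (relative to this sample)*, in the SAP and in all tables and text.
2. Report each quartile's FEV1 % predicted range and median with the results.
3. State that the groups are not COPD stages and that the comparison across diagnosed stages in Protocol section 2.0 was therefore not carried out.
4. Add a supporting analysis in the same FEV1/FVC < 0.70 subset with FEV1 % predicted as a continuous variable. Examples are Spearman rank correlation with the time/funding percentages, and ordinal logistic regression for participation items whose responses are ordered. As the SAP is written in the past tense, mark this as post hoc if the analyses have already been run.

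Items 1 to 3 cost wording, table labels and one descriptive table. Item 4 is a small amount of extra analysis and reporting on a variable that Protocol section 3.0 already has extracted from charts. Its drawback is that it carries the same unconfirmed bronchodilator status as the quartiles.

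### Groups C and D are both labelled high exacerbation risk but use different admission thresholds (≥1 and >1), so a patient with mMRC ≥2 and one exacerbation, hospitalised, belongs to no group

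*SAP*

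**What the plan says.** The SAP, under Statistical Analysis, states that the "groups were based on their mMRC breathlessness scores and 12-month exacerbation history". The labels describe a two-by-two layout, low or high breathlessness by low or high exacerbation risk:

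- **A** (low, low): "mMRC ≤1 with ≤1 exacerbation that did not lead to" hospital admission.
- **B** (high, low): "mMRC ≥ 2 with ≤ 1 exacerbation not leading to hospital admission".
- **C** (low, high): "mMRC ≤ 1 with ≥ 2 exacerbations or ≥ 1 exacerbation that led to hospital admission".
- **D** (high, high): "mMRC score ≥ 2 and ≥ 2 exacerbations or >1 exacerbation that led to hospital admission".

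The grouping is one of five factors in the chi-square tests on each participation item, which compare observed counts with the "statistically expected value for quartiles of airflow obstruction, breathlessness burden and exacerbation risk, sex, age, and PR participation status". For the healthcare and research topics, chi-square and Kruskal-Wallis tests use "healthcare and research topics and airflow obstruction and exacerbation burden and exacerbation risk groups", which appears to be the same grouping under a different name. Neither document restates the definitions or says what happens to a respondent who fits none of the four.

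**The concern.** One label, high exacerbation risk, has two definitions in the same sentence: a single hospitalised exacerbation is enough in C, but more than one is needed in D. B does not take up the difference, because it admits only an exacerbation that did not lead to admission.

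If the printed rule was followed, respondents with high breathlessness and a single, hospitalised exacerbation have no group and leave every comparison that uses the grouping. The loss would not be random. Respondents with the same exacerbation history but low breathlessness would stay in, as members of C, so C and D would differ in how risk was defined as well as in breathlessness. If ≥1 was coded, the results stand and only the text is wrong. A reader cannot tell which of these happened.

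**Working it through.** The SAP gives no figure to reproduce here, so the check is a count of which profiles the four definitions cover.

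**Inputs.** The four definitions come from the SAP, Statistical Analysis. Two ranges are my assumptions: mMRC scored 0 to 4, and 0 to 4 exacerbations in 12 months. Write *e* for exacerbations and *h* for those that led to admission, with 0 ≤ *h* ≤ *e*. Each *or* clause is read as applying within its own mMRC condition, as the labels imply.

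**Profiles.** The number of (*e*, *h*) histories is 1 + 2 + 3 + 4 + 5 = 15. With 5 mMRC scores, 15 × 5 = 75 profiles. Two scores (0, 1) are low breathlessness and three (2, 3, 4) are high.

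**Histories that meet each risk rule**

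- Low risk, A and B (*e* ≤ 1 and *h* = 0): (0,0) and (1,0), so 2.
- High risk as in C (*e* ≥ 2 or *h* ≥ 1): 3 + 4 + 5 = 12 with *e* ≥ 2, plus (1,1), so 13.
- High risk as in D (*e* ≥ 2 or *h* > 1): the same 12 and no more, because *h* > 1 already implies *e* ≥ 2.

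**Coverage**

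| Group | As printed | With C's admission clause in D |
|---|---|---|
| A | 2 × 2 = 4 | 4 |
| B | 3 × 2 = 6 | 6 |
| C | 2 × 13 = 26 | 26 |
| D | 3 × 12 = 36 | 3 × 13 = 39 |
| Placed | 72 | 75 |
| Unplaced | 3 | 0 |
| In two groups | 0 | 0 |

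The three unplaced profiles (mMRC, *e*, *h*) are (2,1,1), (3,1,1) and (4,1,1). The same history at mMRC 0 or 1 falls in C. Allowing up to 10 exacerbations gives 66 × 5 = 330 profiles and leaves the same three unplaced.

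**Redundancy.** In C the admission clause adds two profiles beyond *e* ≥ 2: (0,1,1) and (1,1,1). In D, as printed, it adds none.

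**Other readings of the wording**

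- If A and B count only non-hospitalised exacerbations (*e* − *h* ≤ 1), the three profiles enter B, labelled low risk. But 7 histories × 2 scores fall in both A and C, and 6 × 3 in both B and D: 14 + 18 = 32 of 75 in two groups.
- If the admission clauses in C and D stand free of the mMRC condition, the three profiles enter C despite high breathlessness. Then 6 × 2 + 9 × 3 = 12 + 27 = 39 of 75 fall in both C and D.

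Of these readings of the printed text, only the one used in the table puts no profile in two groups, and it is the one that leaves the gap.

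**The case against.** The strongest reply is that this is a one-character slip with an obvious intention. The >1 is the only strict inequality among the four definitions. A and B share one low-risk rule, and its exact complement is what C states, so the two-by-two layout points to the same rule for D. The sign might even be a ≥ that lost its bar in conversion from the PDF, which a look at the original page would settle. This stands as an argument about intent, and the redundancy of D's clause supports it. It does not settle what was coded. Conversion is also not the obvious explanation, since the other ≥ and ≤ signs in the definitions survived.

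The second reply is about size. One cell is affected, no group counts are given, and 3 of 75 is not a proportion of patients: the denominator moves with the assumed maximum, to 330 at ten exacerbations. This also stands. The enumeration shows that a gap exists and where it is, not how many people are in it. Anyone with mMRC ≥2 and two or more exacerbations still enters D, and the tests by airflow obstruction, sex, age and PR participation do not depend on this grouping. Nothing in the documents shows that any result is wrong.

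**Conclusion.** The concern holds. As printed, C and D define high exacerbation risk differently, and mMRC ≥2 with exactly one exacerbation, hospitalised, fits no group. The contradiction itself is certain on the ordinary reading, in which each *or* clause stays within its mMRC condition; it does not depend on the assumed score or count ranges, which affect only the profile totals.

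The effect on results is unknown. It is nil if ≥1 was coded or if no respondent has this history. If >1 was coded, every such respondent is missing from the participation comparisons by this grouping and, assuming the differently worded grouping is the same one, from those for the healthcare and research topics. The SAP reports the grouping in the past tense, so the coding already exists and can be checked. It should be fixed, because the groups feed many tests and cannot be reproduced with confidence from the text.

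**What to change.** 1. Reconcile C and D to one definition of high exacerbation risk. Wording D's admission clause as in C puts every profile in exactly one group. Bracketing the *or* clauses is an optional drafting aid.
2. State which admission threshold was coded for D.
3. Check that A + B + C + D equals the number of respondents with both mMRC and exacerbation data, and report any who were unplaced.
4. If >1 was coded, reclassify those respondents and re-run the comparisons that use these groups. If ≥1 was coded, correct the text only.

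The cost is one line of SAP text and one check of existing coding, with a re-run of existing comparisons only in the first case. No new data are needed.
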